## Study Protocol

The objective of the proposed music intervention is to standardize the procedures in which the intervention is carried out such that 1) it matches the music intervention in our previous study and that 2) it can be replicated in the future to include new outcome measures.

The data from this intervention will be compared to a control group and we hypothesize that the intervention group will exhibit enhanced post-intervention measurement at 11 months of age in comparison to the control group.

Families with healthy infants with no family history of hearing, speech and communication disorders will be recruited at 7 months of age to participate in the longitudinal music intervention study (Aim 2) that will last for about 4 months. At recruitment, infants with 3 or more ear infections and infants who have already been/ have had participated in infant music classes will be excluded.

Infants will complete a pre-intervention brainstem measures at 7 months of age upon enrolling in the study: the frequency-following response measure (FFR). Participants will have to complete the measurement to proceed to the intervention phase.

The music intervention starts at 9 months of age if the participants completed the pre-intervention measurement at 7 months of age. The 12-session intervention (15 minutes per session) is intended to last for a 4-week period with 3 sessions/week. It can last for as long as 5 weeks if some sessions are missed. Participants have to complete all sessions to be eligible for post-intervention measurements. During each session, a facilitator will guide the caregivers to interact with infants by synchronizing infants' movement to musical beats. At 9 months of age, families will start the 12-session intervention in a controlled laboratory space. In the initial session, caregivers will be given a brief orientation to intervention, including introducing them to the musical toys they will be using during the sessions with their infants and the lab environment. They will also be trained technics through which they can synchronize the infant's movements to the experimenter's movements, such as clapping hand, tapping feet. The remaining sessions will be scheduled in groups of 2-3 infant/parent dyads. In each session, a music CD with 15 minutes of selected children's music will be played and a musically trained experimenter will facilitate the sessions to engage the infants and parents to move to musical beats, using different musical toys, such as infant drums and maracas. Parents will be instructed to not to repeat any of these activities outside of the lab setting for the period of the study. Upon finishing the intervention, infants will repeat the FFR measurement at 11 months of age.

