## Statistical Design and Powers

Our *a priori* power analysis is based on two previous studies in our lab that delivered similar foreign language or music intervention during the same period in development with behavioral/electrophysiological outcome measures post intervention [7,24]. In both studies, the comparisons were only at post-intervention between the intervention group and the control group. In the language intervention study, the intervention group exhibited higher consonant discrimination ( $M=65.7$ ,  $SE=2.4$ ) than control ( $M=56.7$ ,  $SE=2.3$ ) and in the music intervention, the main effect of intervention in the ANOVA model had an effect size  $\eta^2$  of 0.12. Using the G\*Power software, it shows that to detect a similar between group effect, a total of 40 subjects at a level significance level of 0.05 will yield power above 0.90.

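### No primary analysis model is named and the 7-month FFR serves only as an entry condition; a pre-stated ANCOVA would use it, provided control infants have it too

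*Combined protocol and SAP*

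**What the plan says.** In the Study Protocol section the hypothesis is that "the intervention group will exhibit enhanced post-intervention measurement at 11 months of age in comparison to the control group". The same section schedules the FFR twice. The first is at enrolment: "Infants will complete a pre-intervention brainstem measures at 7 months of age upon enrolling in the study". The second follows the intervention: "infants will repeat the FFR measurement at 11 months of age".

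The one use given for the 7-month value is as a gate: "Participants will have to complete the measurement to proceed to the intervention phase". The description of the intervention repeats the condition, with the start at 9 months applying "if the participants completed the pre-intervention measurement at 7 months of age".

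Statistical Design and Powers is the only statistical section. Of the two earlier studies it draws on, it says that "the comparisons were only at post-intervention between the intervention group and the control group". It then sizes this study "to detect a similar between group effect, a total of 40 subjects". The ANOVA mentioned there belongs to the earlier music study. For this study no model, test, sidedness or covariate is given. The documents also give no visit schedule for control infants and no method of allocation.

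**The concern.** The earlier studies compared groups only after the intervention. This study adds a pre-intervention measurement of the same kind as the outcome, yet the hypothesis and the power section still describe an 11-month group comparison. If the analysis follows that framing, the 7-month value is collected and then left out of the comparison.

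Two things are at stake. The first is precision. With 40 infants in total, a baseline that is moderately correlated with the outcome removes a worthwhile share of the residual variance. The second is error control. With no model on record, the unadjusted and the adjusted result could both be computed and the more favourable one reported.

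**Working it through.** **Inputs from the documents** (Statistical Design and Powers): 40 infants in total, significance level 0.05, eta-squared 0.12 from the earlier music study.

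**Assumptions not in the documents:** 20 per group; eta-squared that of a two-group comparison (or a partial eta-squared); equal variances; a 7-to-11-month correlation rho, shown over a range. Sidedness is not stated, so both cases are shown. Clustering in sessions of 2-3 dyads, and loss of infants who do not complete all sessions, are ignored.

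**Effect size.** f = sqrt(0.12/0.88) = 0.369; d = 2f = 0.739.

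**The plan's own figure.** For an unadjusted comparison, the noncentrality is (20/2) × d² = 10 × 0.5455 = 5.455 on 1 and 38 df. Power is 0.624 two-sided and 0.742 one-sided, so power above 0.90 is not reproduced from this input. Two-sided power reaches 0.904 with 40 per group (80 in total). The language study cannot be checked because its group sizes are not given. Its mean difference is 65.7 − 56.7 = 9.0, and its SD would be sqrt((2.4² + 2.3²)/2 × m) for m infants per earlier group. At m = 13 that gives d = 1.06 and two-sided power 0.905; at m = 20, d = 0.86 and 0.751.

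**ANCOVA.** The residual variance is multiplied by 1 − rho². The noncentrality becomes 10d² / [(1 − rho²)(1 + t²/38)] on 1 and 37 df, averaged over t with 38 df to allow for chance baseline imbalance. At rho 0.5, before the imbalance term, it is 5.455/0.75 = 7.27.

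| Analysis | Two-sided power | One-sided power |
|---|---|---|
| Unadjusted | 0.624 | 0.742 |
| ANCOVA, rho 0 | 0.612 | 0.731 |
| ANCOVA, rho 0.3 | 0.653 | 0.766 |
| ANCOVA, rho 0.5 | 0.736 | 0.833 |
| ANCOVA, rho 0.7 | 0.881 | 0.936 |

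- Cost at rho 0: 0.624 − 0.612 = 0.012 two-sided; 0.742 − 0.731 = 0.011 one-sided.
- Two-sided gain: 0.03 at rho 0.3, 0.11 at 0.5, 0.26 at 0.7. One-sided gain: 0.02, 0.09 and 0.19.
- Two-sided break-even is at rho of about 0.17.
- Power 0.90 at 40 infants needs rho of about 0.72 two-sided or about 0.63 one-sided.

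**Error rate if the choice is made on the results.** In 100,000 simulated null trials of 20 per group, each test alone rejects in about 0.05. If a finding is claimed when either the unadjusted or the adjusted two-sided test is significant, the rate is 0.064, 0.072 and 0.082 at rho 0.3, 0.5 and 0.7.

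**The case against.** The strongest reply is that the plan does imply an analysis. The hypothesis and the power section together describe an 11-month group comparison, which is valid even if less efficient, and the quoted hypothesis contains no error. That largely stands. The point is a missing model statement and an unused measurement, not an invalid comparison.

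Second, the benefit rests on a correlation that the documents do not give, between measurements four months apart. That also stands. A material gain needs rho of about 0.5 or more, and nothing in the documents supports any particular value. The gain is smaller, too, if the language-study effect is the relevant one: at d = 1.06 and rho 0.3, two-sided power rises only from 0.905 to 0.922. What remains is the asymmetry between a cost of about one point and a possible gain of 0.11 or more.

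Third, ANCOVA is only one option, and pre-stating any single analysis would deal with error control. True, and if groups are not randomised, ANCOVA and a change-score analysis can answer different questions. On efficiency, though, a change score is weaker over this range: with equal variances at both ages its two-sided power is 0.363, 0.486, 0.624 and 0.836 at rho 0, 0.3, 0.5 and 0.7.

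Fourth, control infants may have no 7-month FFR. The enrolment sentence is general, but the gate and the repeat measurement are described along the intervention path. The documents do not settle this, so it has to be a proviso.

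**Conclusion.** The point holds in limited form. The plan frames an 11-month comparison of intervention with control, names no model, and gives the 7-month FFR no analytic role. A pre-stated ANCOVA is the better method if control infants have the baseline. On the assumptions listed, the change in two-sided power runs from a loss of about one point at rho 0 to gains of 0.03, 0.11 and 0.26 at rho 0.3, 0.5 and 0.7.

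A reader might infer more, in three ways that the documents do not support:

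- *That the plan rules out baseline adjustment.* It neither excludes it nor commits to it.
- *That the false-positive rate of this trial is already above 0.05.* The range 0.064 to 0.082 applies only if whichever of the two results is significant were reported, and nothing says that it would be.
- *That adjustment makes good the stated power above 0.90.* Under the music-study effect this needs rho of about 0.72 two-sided or 0.63 one-sided, and no correlation is given. The failure to reproduce that power is a separate issue, which exists with or without ANCOVA.

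The naming of the primary FFR measure and the method of allocation are also separate gaps. They matter here because the covariate must be the same measure as the outcome, and because adjustment for one baseline value does not by itself remove confounding between non-randomised groups.

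**What to change.** State in Statistical Design and Powers: *The primary analysis is an ANCOVA of the 11-month value of the primary FFR measure on group, with the 7-month value of the same measure as covariate; the adjusted group difference is tested at the 0.05 level.* Name the measure and state the sidedness.

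State the control group's schedule, confirming that control infants complete the FFR at both 7 and 11 months. State how infants are allocated. If allocation is not randomised, describe the adjusted difference as possibly still confounded. Do not cite the adjustment in support of power above 0.90 unless a correlation is given to justify it.

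If control infants already have the 7-month FFR, the change is to wording only, at a cost of about one point of power should rho be near 0. If they do not, they would need an added 7-month visit, which is not a small change. In that case, pre-state the unadjusted 11-month comparison as the single primary analysis.

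### The 11-month FFR is measured only in infants who finish every session, so the group comparison is open to selection by completion unless controls face an equivalent rule

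*Combined protocol and SAP*

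**What the plan says.** All of this is in the Study Protocol section unless noted.

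- **Baseline.** "Infants will complete a pre-intervention brainstem measures at 7 months of age upon enrolling in the study", and "Participants will have to complete the measurement to proceed to the intervention phase".
- **Entry to music.** "The music intervention starts at 9 months of age if the participants completed the pre-intervention measurement at 7 months of age".
- **Sessions.** There are 12, planned at three a week over four weeks. The window can stretch: "It can last for as long as 5 weeks if some sessions are missed".
- **Outcome eligibility.** "Participants have to complete all sessions to be eligible for post-intervention measurements".
- **Hypothesis.** "the intervention group will exhibit enhanced post-intervention measurement at 11 months of age in comparison to the control group".
- **Size.** Statistical Design and Powers gives only a total: "a total of 40 subjects at a level significance level of 0.05 will yield power above 0.90".

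The text names a control group. It does not say what controls do between 7 and 11 months, whether any attendance condition applies to them, where they come from or how infants are assigned. No analysis model is given that uses the 7-month FFR when the groups are compared.

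**The concern.** The eligibility rule decides whose outcome is collected, not merely which analysis set an infant belongs to. If a music infant misses a session that is not made up, no 11-month FFR exists for that infant, and no later analysis can recover the comparison of everyone who started.

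Families who keep 12 appointments in four or five weeks may differ from those who do not, for example in infant health, parental time or the home environment. If such a trait is related to the FFR and only the music group is screened on it, the 11-month contrast mixes any music effect with the difference between completers and everyone else. Randomisation does not protect against this, because the screening happens after assignment. The direction of the bias follows the sign of the link between completing and the FFR. The 7-month FFR, already collected on enrolment, could absorb part of it, but the text does not say that it enters the comparison.

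**Working it through.** **1. The rule, group by group.** In the music group, 12 sessions are described and the 11-month FFR requires all of them. In the control group, no sessions are described. Taken literally, a rule about sessions would shut out controls who have none. Since a control measurement at 11 months is clearly intended, the rule must either act on music alone or have an unstated counterpart for controls.

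**2. The plan's power figure.** The prior music study's eta squared is 0.12. Then f = √(0.12/0.88) = 0.369 and d = 2f = 0.739 for two equal groups. With an assumed 20 vs 20, two-sided 0.05, the noncentrality is 0.739/√(1/20 + 1/20) = 2.34 and power is 0.62, so this input does not reproduce a figure above 0.90. The language study might, but its group sizes are not given. That is a separate question. Here d only prices the fix.

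**3. Illustrative bias, no true effect.** Assumptions: 20 allocated per group, all controls measured, a share c of music infants completing, and completion fully determined by a normal trait correlated r with the FFR. Bias in SD units = r × φ(q)/c, where q is the normal cut-point that leaves a share c above it.

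| Completers | φ(q)/c | Bias, r = 0.3 | Bias, r = 0.5 | Type I error (simulated) |
|---|---|---|---|---|
| 16 of 20 | 0.280/0.80 = 0.350 | 0.105 | 0.175 | 0.061 to 0.081 |
| 13 of 20 | 0.370/0.65 = 0.570 | 0.171 | 0.285 | about 0.07 to 0.12 |

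Variants:
- 19 of 20 completing: 0.052 to 0.055.
- Completion correlated only 0.5 with the trait: 0.052 to 0.059 (16 completers) and 0.055 to 0.067 (13).
- Adjusted for a 7-month FFR that also depends on the trait and correlates 0.5 with the outcome: 0.053 to 0.062 (16) and 0.058 to 0.072 (13).
- Both groups filtered alike: mean bias about zero.

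**4. Completion rate.** None is given. If make-ups are held to three a week, five weeks give 15 slots, and 80% or 90% attendance per slot gives 65% or 94% completing. One extra slot changes this to 80% or 98%. The text sets no such cap, so these are assumptions.

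**5. If non-completers are invited but only half return.** With 16 completers, non-completers average −r × 0.350 × 16/4 = −1.40r. Adding two of them leaves (16 × 0.350 − 2 × 1.40)r/18 = 0.156r, or 0.05 to 0.08 SD. With 13 completers, the same arithmetic leaves (13 × 0.570 − 3.5 × 1.06)r/16.5 = 0.22r, or about 0.07 to 0.11 SD. The bias shrinks but remains.

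**6. Power cost of measuring everyone.** Assumptions: d = 0.739, 80% completing, no effect at all in non-completers (worst case), and correlation 0.5 between the two FFRs when adjusting.

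| Comparison | Unadjusted | Adjusted (effect ÷ √0.75) |
|---|---|---|
| 16 completers vs 20 | d 0.739: 0.57 | d 0.853: 0.69 |
| All 20 vs 20 | 0.8 × 0.739 = 0.591: 0.44 | 0.682: 0.56 |

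Like for like, dilution costs about 0.13 in power in either column. Adjustment raises both rows, so it does not cancel the dilution.

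**The case against.** The strongest reply is that the control group's activity is simply not described. Controls might attend sessions of their own, and the word participants could bind both groups. An identical filter in both groups leaves about zero mean bias. This stands, and it is why the point is conditional. It does not clear the plan: no such sessions are stated, and a completers-only comparison would still not be a comparison of the groups as formed.

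A second reply is that the illustration needs completion to be wholly driven by a trait linked to a brainstem response, which nothing in the documents supports. This also stands. With a weaker link or near-complete attendance, the error rate is close to 5%. The point rests on the rule, not on these figures.

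A third is that full exposure is a defensible target for a study meant to standardise an intervention. That supports keeping a completers analysis. It does not support declining to collect the other infants' outcomes.

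A reader might go further and infer that the study is not randomised, because the only written route runs from the 7-month FFR to music. The documents do not support that. The text describes the music procedure ("recruited at 7 months of age to participate in the longitudinal music intervention study (Aim 2"), names a control group, and is not the whole of the study's documentation. Assignment may be set out elsewhere, and silence here shows only that it cannot be confirmed.

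**Conclusion.** The concern holds in conditional form. The plan ties outcome collection to completing all 12 sessions. Unless controls are subject to an equivalent rule, the 11-month contrast compares selected music infants with unselected controls, whether or not infants are randomised. No stated use of the 7-month FFR limits the effect.

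The size cannot be derived, because neither the completion rate nor its link with the FFR is given. Under the strong assumptions above, type I error would be about 6% to 8% with 16 of 20 completing and 7% to 12% with 13 of 20. Under mild ones it would be near 5%. These figures assume a 20 vs 20 split and two-sided testing, neither of which the plan states. The change is worth making because it is cheap and the lost outcomes cannot be recovered later, not because serious inflation has been shown.

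The missing control source and assignment method call for clarification only and do not carry this finding.

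**What to change.** 1. **Replace the outcome-eligibility rule** (cheap). Suggested text: *The 11-month FFR is offered to every infant in both groups who completed the 7-month FFR, regardless of sessions attended. The comparison of all infants by group is primary; infants who completed all sessions are a secondary analysis.* This changes who is measured, not how the sessions are delivered. If controls have no 7-month FFR, define their set by entry to the control group.
2. **Add the covariate** (free for infants already measured at 7 months). *Groups are compared on the 11-month FFR adjusted for the 7-month FFR*, wherever controls have one.
3. **Clarify the control group.** State, or cross-reference, its source, its activity, any attendance condition and the method of assignment. If controls are not randomised, report the result as a non-randomised association.

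**Cost.** There would be a few extra visits by non-completers. Some may not return, in which case the bias is reduced rather than removed. Possible dilution costs power as shown above, in the assumed worst case from 0.57 to 0.44 unadjusted or from 0.69 to 0.56 adjusted. In a study of 40 that price is real and should be accepted knowingly. It shrinks as completion rises or if partial attendance has some effect.

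### Only infants who complete all 12 music sessions get the 11-month FFR, so non-completers have no outcome and the comparison with control can be biased

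*Combined protocol and SAP*

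**What the plan says.** All the relevant text on conduct is in the Study Protocol section.

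- **Entry to the music phase.** "The music intervention starts at 9 months of age if the participants completed the pre-intervention measurement at 7 months of age". Every music infant therefore has a 7-month FFR.
- **Schedule.** "The 12-session intervention (15 minutes per session) is intended to last for a 4-week period with 3 sessions/week".
- **Missed sessions.** "It can last for as long as 5 weeks if some sessions are missed". Nothing is said about infants who are still short of 12 sessions after that.
- **Condition for the outcome.** "Participants have to complete all sessions to be eligible for post-intervention measurements".
- **Outcome.** "Upon finishing the intervention, infants will repeat the FFR measurement at 11 months of age".
- **Hypothesis.** "we hypothesize that the intervention group will exhibit enhanced post-intervention measurement at 11 months of age in comparison to the control group".

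The only sessions described are music sessions. The documents do not give a schedule or completion rule for controls, the method of allocation, an analysis population, a method for missing data or an allowance for dropout.

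**The concern.** The rule selects infants on something that happens after they enter the music phase. Attendance at three laboratory visits a week may reflect infant health, temperament or family circumstances, and each of these may also relate to the FFR. If so, the difference between music completers and controls mixes the effect of music with the selection of completers.

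This is more than a choice of analysis set. An analysis set can be changed later if the data exist. Here the non-completers' outcomes are never recorded, so an analysis by original group would have to fill them in by modelling or imputation, on assumptions that the trial's data cannot test.

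The 7-month FFR is only a partial safeguard. Adjusting for it may remove some, all or none of the selection, or increase it, depending on how completion relates to the baseline value.

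**Working it through.** **Inputs from the documents.** Twelve sessions, three a week, at most five weeks (Study Protocol). Total of 40 infants, significance level 0.05, eta-squared 0.12 from the earlier music study (Statistical Design and Powers).

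**Assumptions, none given in the documents.** 20 infants per group; two-sided test; no true effect when bias is computed; completion propensity and 11-month FFR bivariate normal with correlation ρ = 0.3; 15 available slots (5 weeks × 3) with independent attendance.

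**The plan's own figure.** The plan states that "a total of 40 subjects at a level significance level of 0.05 will yield power above 0.90". Eta-squared 0.12 gives d = 2√(0.12/0.88) = 0.739. With 20 per group, the noncentral t gives power 0.62; 0.90 needs about 40 per group. That discrepancy is a separate matter and this point does not depend on it, but it explains why the power figures below are near 60%.

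**1. Non-completion.** q = 1 − P(Bin(15, p) ≥ 12), where p is the chance of attending a slot.
- p = 0.90: q = 0.056
- p = 0.85: q = 0.177
- q = 0.25 is added as an assumed higher value.

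**2. Bias with all controls measured.** Bias = ρ·L(q), with L(q) = φ(z_q)/(1 − q). For q = 0.177, z = −0.927 and φ = 0.260, so L = 0.260/0.823 = 0.315 and the bias is 0.3 × 0.315 = 0.095 SD. The standard error is √(1/(20(1 − q)) + 1/20), and type I error comes from the noncentral t.

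| q | Bias (SD) | SE | Bias/SE | Type I error | Bias/0.739 |
|---|---|---|---|---|---|
| 0.056 | 0.036 | 0.321 | 0.11 | 5.1% | 5% |
| 0.177 | 0.095 | 0.333 | 0.28 | 5.9% | 13% |
| 0.25 | 0.127 | 0.342 | 0.37 | 6.5% | 17% |

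**3. Controls under an equivalent rule.** Bias = 0.3·(L(q_music) − L(q_control)).
- Equal non-completion: zero.
- 18% music, 6% control: 0.06 SD, type I error 5.3%. With the rates reversed: −0.06 SD.
- 25% music, 6% control: 0.09 SD, 5.8%.

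**4. Other correlations, controls fully measured.**
- ρ = 0: no bias.
- ρ = 0.1, q = 0.177: 0.03 SD, 5.1%.
- ρ = −0.3: same size as in step 2, opposite sign.
- ρ = 0.5 with 20% to 40% loss: 0.17 to 0.32 SD, type I error 8% to 14% (simulated).

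**5. Adjusting for the 7-month FFR.** Assume a correlation of 0.5 between the 7- and 11-month FFR. The residual bias is (0.3 − 0.5·ρ_x)·L(q), where ρ_x is the correlation of completion with the 7-month FFR. At q = 0.177:

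| ρ_x | Residual bias (SD) | Share of unadjusted bias |
|---|---|---|
| 0.6 | 0 | 0% |
| 0.3 | 0.047 | 50% |
| 0 | 0.095 | 100% |
| −0.3 | 0.142 | 150% |

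**6. Cost of including non-completers.** At p = 0.85, non-completers attend 10.5 of 12 sessions on average.
- Benefit proportional to sessions: d = 0.739 × (0.823 + 0.177 × 10.53/12) = 0.72; power 61% with 20 v 20.
- No benefit in non-completers: d = 0.739 × 0.823 = 0.61; power 47%.
- Completers only, 16.5 v 20, d = 0.739: power 58%.

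**7. Sensitivity to the number of slots.** The plan does not cap make-ups at three a week. At p = 0.85, 18 slots give q = 1.2% and 20 slots give 0.1%. With 18 slots, L is about 0.031 and the bias is 0.3 × 0.031 = 0.009 SD.

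**The case against.** The strongest reply is that the harm is small and may be close to nil. In the main illustration type I error rises by at most 1.5 percentage points (6.5% − 5.0%), and the larger figures need loss rates and correlations that nothing in the documents supports. The slot count matters most: if families can reschedule freely within five weeks, almost everyone completes. This stands as a limit on the size. It does not change what happens to an infant who still falls short, and if such infants are few, measuring them costs almost nothing.

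A second reply is that the effect of the full programme is a legitimate target, and the plan wants the intervention to match its previous study. The target is coherent. The matching aim, however, concerns how the intervention is delivered; it does not make a completers-only comparison the stated objective. Completers against controls is also not a clean full-dose effect if completers differ from other infants. The full-dose comparison remains available as a secondary analysis.

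Third, including non-completers can cost power: 47% against 58% if they gain nothing. That is a real cost in the unfavourable case. Under proportional benefit, power is slightly higher (61% against 58%).

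Last, if groups are not randomised, selection at entry could outweigh this one. Allocation is not described, so this cannot be judged; the fix reduces selection but does not remove it.

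**Conclusion.** The concern holds. As written, the plan leaves every music infant short of 12 sessions without an 11-month FFR, and no other text provides for measuring them. The comparison with control can then be biased if non-completers differ in expected FFR or, should controls face a similar rule, if non-completion or its relation to the FFR differs between groups.

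The likely size is modest: 0.04 to 0.13 SD under the main assumptions, which is 5% to 17% of the effect implied by eta-squared 0.12. It is zero if completion is unrelated to the FFR or if everyone completes, and larger under stronger assumptions. These figures are examples, not bounds; the true size and direction cannot be derived from the documents. The point should be fixed because the existence of the rule is certain, the lost outcomes cannot be recovered after data collection, and the change is cheap.

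**What to change.** Replace the eligibility sentence with wording such as: *All infants who enter the music or control group are invited for the 11-month FFR, whatever number of sessions they attended; the number attended is recorded.* Then:

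- Make the primary comparison by original group in all infants with an 11-month FFR, adjusting for the 7-month FFR if it was measured in both groups.
- Keep the 12-session completers as a secondary per-protocol analysis.
- Report the number of non-completers by group, with their 7-month FFR, where measured, beside that of completers.
- State how infants are allocated and whether controls have any sessions or completion rule, because the primary comparison depends on both.

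The cost is about 1 to 5 extra recordings per 20 music infants at 6% to 25% non-completion (20 × 0.06 = 1.2; 20 × 0.25 = 5), plus some dilution by partly exposed infants. The 12-session intervention itself does not change. Some selection will remain if families who miss sessions also miss the visit.
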